## 10.4. Follow-up Assessments

The following assessments will take place at 3 and 6 months since randomization:

- *Self-reported adherence behaviors (Voils)*
- *Objectively assessed adherence*
- *Cognitive assessment battery*
- *Social support*
- *Depression*
- *Mindfulness (MAIA and FFM)*
- *Sleep Quality (PSQI)*
- *Physical capacity (walking test)*
- *Weight, height, hip and waist measurements*
- *Blood pressure*
- *Acceptability.* To assess acceptability we will use the intervention enjoyment scale used in a previous study. We will ask participants to rate the intervention on a scale from 0 to 4.
- *Attendance* at classes will be recorded at each session by the instructor using a mindfulness attendance log.
- *Individual mindfulness practice* at home will be self-reported by means of a diary to be kept daily. Logs will be collected in person at follow-up visits.
- *Program evaluation* will be determined using a standardized form we used in previous studies.

In response to the COVID-19 pandemic, and due to the fact that this is a high-risk population, BP will be self-measured at the planned assessed date and self-reported values will be communicated to the RA over the phone. This will be noted in the Access database and in future manuscripts and scientific reports.

## 11 DATA COLLECTION

### 11.1. Data sources

Data will be collected and using pre-tested and validated forms, which have been found to be acceptable by the type of individuals who will participate in this project. Information about medical history, hospital readmissions or unplanned clinic visits will be collected from electronic medical records or directly from the patient's primary care physician or cardiologist using previously designed abstraction forms. We will develop electronic versions of each study form and data abstraction form for data entry using RedCap technology.

### 11.2. Data safety

Electronic data will be stored in password protected data files accessible only to authorized project personnel including the Principal Investigator, Data Systems Analyst, Statisticians and SRA. All data files will be automatically backed up daily. Paper data will be stored in locked file cabinets. Data containing identifiers (e.g., name, address, phone number of participants from ACCESS files) will be stored on password-protected secure servers separately from de-identified study data (e.g., surveys, screeners).

### **11.3. Data collection**

The RA will collect data via in-person interviews at each data collection point. In response to the COVID-19 pandemic, and due to the fact that this is a high-risk population, follow-up assessments will now be completed over the telephone, via video-conference (using secure, HIPAA compliant videoconferencing software), or by mailing study surveys (that will be returned using pre-stamped envelopes) depending on the participant preference and internet accessibility. Research Electronic Data capture (REDCap) technology will be used to for direct data entry in electronic CRFs during the interviews; clinical data will be entered by the RA from the abstraction forms into electronic version of the abstraction forms in REDCap. Any ambiguity in the response to a question will be brought to the attention of the Data Systems Analysts for clarification. If the Data Systems Analyst is unsure how to code the response, the matter will be brought to the attention of the PI. The Data Systems Analyst will maintain a log so that future occurrences of problems will be handled in the same manner.

## **12**

## **DATA MANAGEMENT**

### **12.1. Tracking Systems**

Prior to beginning subject recruitment; the Data Systems Analyst will develop a tracking system using Access software. The tracking system is essentially a reminder and participant tracking system to aid the study RA in ensuring that all procedures are followed, treatment are adhered to, and assessments administered in a timely fashion. The tracking system will include all steps included within the Recruitment, Treatment and Follow up phases of subject participation in the trial. Quantitative data will be entered into an Access database where they will be stored for cleaning.

### **12.2. Data entry and storage**

Our major data management and analysis needs for the proposed project can be met by using a Pentium-based microcomputer. The data systems analyst will conduct data management under the supervision of the study biostatistician and the PI. De-identified data will be exported directly through the REDCap interface into study datasets. STATA©10, Statacorp-LP statistical software will be used for statistical analyses.

Electronic data will be stored in password protected data files accessible only to authorized project personnel including the Principal Investigator, Data Systems Analyst, Statisticians and RA. All data files will be automatically backed up daily. Paper data will be stored in locked file cabinets. Data containing identifiers (e.g., name, address, phone number of participants from ACCESS files) will be stored on password-protected secure servers separately from de-identified study data (e.g., surveys, screeners).

The Data Systems Analyst will work with project statistician [name] and the PI to ensure that data are cleaned prior to analysis. When ready for analysis, he will provide a SAS database of collected data to the statistician.

### 13.1. Treatment Fidelity

Assessments of treatment fidelity will be performed following the guidelines developed by the Treatment Fidelity Workgroup. During the start-up period, auditor checklists will be created and used to monitor fidelity to the intervention. Checklists will be reviewed weekly by [name] who will oversee treatment fidelity procedures. Optimal treatment fidelity would be evidenced by 100% of objectives met. If less than 85% of treatment-specific objectives are met, the auditor will remediate instructor's training as needed.

### 13.2. Training

Staff involved in data collection will be trained and certified regarding their competence. The RA will receive extensive training in the administration of cognitive tests by [name] prior to study inception. This includes training on administration and scoring of all questionnaires as well as on review assessment instruments immediately for omissions. When information is missing or incomplete, the RA will contact participants to obtain the necessary information. *A manual of procedures* will be developed during the study start-up period that explicitly describes the specific procedures related to data collection and quality assurance. At study beginning, the first 10 subjects will have their data audited to make sure there are not any systematic problems with regards to entry. This preliminary audit process will reveal any possible problems at the onset as opposed to the end of the study which would result in more work cleaning the data.

### 13.3. Data monitoring

Under supervision from the PI and the Biostatistician ([name]), the Data Systems Analysts ([name]) will ensure that entered data accurately represent data collected. She will conduct error-checking procedures quarterly on all data to ensure their accuracy. Data entry systems developed using Access will include appropriate skip patterns and parameter limits to ensure that data are entered accurately (e.g., item response formats from 1-5 will not permit entry of other numbers). Data entry systems will be tested to ensure that these constraints are working correctly prior to entering real data. REDCap employs automatic checks for values that are out of range or represent errors of logic. Outliers will be corrected if possible with verification from participants.

Quantitative data will be cleaned prior to analysis and then made available to the study statisticians for analysis. [name] will be primarily responsible for the final outcome analyses and will assist in the preparation of manuscripts and reports.

### 13.4. Metrics

All data designated as primary outcome data will be subject to a 100% cross-referencing with the original paper copy. This audit must have an error rate less than 1%. If the verification fails the audit, all data will be re-entered, the original computer files discarded, and the newly re-entered data audited. This process will continue until the audit no longer exceeds the maximum allowable error rate. All audits will be supervised and documented by the study's Data Systems Analyst.

All other entered information (non-primary outcome data) will be subject to a 20% sample that will be cross-referenced with the original paper copy. This audit must have an error rate less than 1%. If the sample fails the audit, all data will be verified against the paper originals. If the error rate of the complete audit is greater than 1% then all data will be re-entered, the original computer files discarded, and the newly re-entered data audited. This process will continue until the audit no longer exceeds the maximum allowable error rate. At the discretion of the study's Principal Investigator, the full audit may be omitted in favor of a complete re-entry of the original paper data. All audits will be supervised and documented by the study's Data Systems Analyst.

## 14

## STATISTICAL CONSIDERATIONS

### 14.1. Preliminary analyses

Preliminary analyses will examine comparability of participants at baseline on demographic and other characteristics using Fisher or t-tests depending on the specific variable characteristics (categorical or continuous). We will examine the distributional properties of continuous variables to determine if normalizing transformations should be applied before conducting further analyses. If group differences are found for any variables, we will evaluate them and statistically control them in outcome analyses (e.g., employing them as covariates in linear or logistic regression analyses to control for their effects on the outcomes). After all the data have been collected, and before conducting the final outcome analyses, we will explore the relationship of several key variables that could impact the outcome, such as participant attendance and number of study contacts during the study. If there are group differences on these variables and/or there are relationships of these variables to the outcomes, we will include them as covariates in our analyses.

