person by the RA in a private room at the CBPM after a thorough explanation of the study design, of the study intervention, and of the risks and benefits involved. Since the study requires access to protected health information (PHI), HIPAA authorization will be required from each individual in order to access his or her medical records. Signed informed consent forms will be kept in locked filing cabinets separate from all data. Participants will receive a copy of the consent for their records. *Once informed consent procedures are completed*, participants will undergo a battery of screening assessments (described in section 9.2). The RA will complete a screening log checking that all eligibility criteria are met at this point.

Screening failures: Microsoft ACCESS© will be used for tracking all participants who expressed interest in participating and were screened for eligibility. We will collect data from all individuals assessed for eligibility (i.e., individuals who consented but then resulted non-eligible at the completion of the screening process) so that we can provide a complete Consort diagram and description of the recruitment process both for publication purposes and as an indicator of future generalizability of the study. We estimate that our screen failure rates will be ~30%, and that 70% of screened participants will be eligible for this study.

Screening window. We anticipate that the time between the completion of all screening procedures and the beginning of the intervention will not exceed 4 weeks. In case > 4 weeks have lapsed, patients will be re-contacted and re-assessed for eligibility.

Randomization. n/a. This is a pre-post design study. NO randomization is involved.

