## **9.2. Design Overview**

This is a pilot study use a pre-test/post-test design. The overall duration of this study will be 2 years; each individual (n=50) will be involved for 6 months. Assessments will be conducted at baseline, end of treatment, and 6- months after baseline.

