## **9.3. Study Intervention**

Intervention setting. Intervention sessions will be individually delivered over the phone. Prior to the beginning of the intervention instructors will contact participants to set up the best time to deliver the intervention.

Session frequency. Participants will receive a 30-minute phone call session once a week for 8 weeks.

Mindfulness training (MT). The intervention protocol is based on the MT protocol pilot-tested in our preliminary work (see Appendix 1 for a script of each session). This intervention maintains the basic components of Mindfulness Based Stress Reduction (MBSR) but has been streamlined to distill the active ingredients for phone delivery. The MT intervention involves training in the following practices: (1) Awareness of breath, a technique in which trainees learn to attend to the sensations associated with breathing; and (2) Body scan, a technique based on the cultivation of attention to bodily sensations that would normally go unnoticed. Later, participants are gradually trained to (3) direct their attention to simple activities of daily life and (4) to become aware of their own thoughts and emotions. Only at the final session they (5) practice “open awareness” – a technique by which the participant is invited to direct his/her attention to any event arising in their field of experience at a given moment, whatever it may be, e.g., a physical sensation, sound, emotion, or thought.

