### 14.3. Secondary Outcomes

To obtain effects of MT on adherence and functional capacity, we will use a series of generalized linear models (GLMs), in which secondary outcome measures will be regressed on time, baseline value of the outcome and potential confounders (i.e., gender, disease severity, social support). Standardized estimates will allow for comparison across different measures of adherence. GLMs

allow for a flexible group of outcome distributions (e.g., binary, continuous); model specification includes determining the distribution and appropriate link function. We will use GLMs to explore changes over time in potential mediators (cognitive function, mindfulness and depressive symptoms) and, in a separate set of models, whether changes in these constructs are associated with changes in secondary outcome variables (adherence and functional capacity). Interest is in gaining estimates of effect for both of these potential pathways. We will also assess potential moderating effects of baseline levels of adherence on our adherence outcomes.

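### Section 14.1 adjusts for undefined group differences and lets post-baseline attendance and study contacts into the Aim 2 models on the strength of their association with the outcome

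*Combined protocol and SAP*

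**What the plan says.** Sections 8.2 and 9.2 describe one group followed over time: "This is a pre-post design study. NO randomization is involved" and "This is a pilot study use a pre-test/post-test design". Everyone is offered the same programme: "Participants will receive a 30-minute phone call session once a week for 8 weeks".

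Section 14.1 nevertheless opens with a comparison: "Preliminary analyses will examine comparability of participants at baseline on demographic and other characteristics using Fisher or t-tests". It continues: "If group differences are found for any variables, we will evaluate them and statistically control them in outcome analyses". It names no groups.

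It then sets a second step, to be taken after data collection is complete and before the final outcome analyses. Variables that might affect the outcome, with attendance and the count of study contacts as examples, are examined. If they differ between groups "and/or there are relationships of these variables to the outcomes, we will include them as covariates in our analyses".

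Section 14.3 gives its own specification for the secondary outcomes: a generalized linear model on time, the baseline value of the outcome, and "potential confounders (i.e., gender, disease severity, social support"). Attendance and contacts are not in that list, and neither section says how the two rules combine. Section 9.1 lists session attendance among the primary feasibility metrics, and section 14.2 sets a 70% attendance criterion.

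**The concern.** Three things are wrong with the rule as written.

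- The first trigger has no referent. With one group and none defined, an analyst cannot tell what the Fisher and t-tests compare. The language reads as carried over from a multi-arm trial, as do the mention of more than one dose in section 14.2 and of time since randomization in section 10.4.
- The second trigger looks at the outcome. Because the two conditions are joined by and/or, association with the outcome is enough to admit a covariate. Doing this before the final analysis gives no protection, since the screen itself uses the outcome data. Analyst blinding to exposure (section 9.5) gives none either, since every participant is exposed. No threshold, closed candidate list or coding is given.
- The named candidates arise after baseline. Attendance is how much of the programme a participant received, so conditioning on it can change what the pre-post estimate means.

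At stake is the Aim 2 estimate of change in adherence and functional capacity, which is meant to inform a later randomised trial. With no control arm, a model fixed in advance is one of the few safeguards available.

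**Working it through.** **The plan's own figure.** Section 14.4 states 80% power at n = 50, two-sided α = 0.05, but gives no effect size or SD on the change scale. For a one-sample test of mean change, the detectable standardised change is (1.960 + 0.842)/√50 = 0.396 (0.404 with the t distribution). The 80% can be neither confirmed nor refuted, but a true change of 0.40 SD is a fair test case because it gives about 80% power at this n.

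**Assumed inputs (not in the documents).** SD of change about 1; sessions attended binomial with 8 trials and probability 0.75, so mean 6 and variance 8 × 0.75 × 0.25 = 1.5; the whole 0.40 SD change produced through sessions, so 0.40/6 = 0.067 SD per session; screening threshold p<0.05.

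**What an uncentred attendance term does to the intercept of a change model.**

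- Without attendance: estimate 0.40, SE 1/√50 = 0.14.
- With raw attendance, the intercept is the change at zero sessions: 0.40 − 0.067 × 6 ≈ 0.
- Its SE is √(1/50 + 6²/(49 × 1.5)) = √(0.020 + 0.490) = 0.71, about five times larger.

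**Simulation, 4,000 trials of n = 50.**

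| Analysis | Mean estimate | SD of estimate | Significant |
|---|---|---|---|
| No attendance term | 0.40 | 0.14 | 78% |
| Raw attendance always added | −0.02 | 0.73 | 5% |
| Centred attendance | 0.40 | – | 78% |
| Raw attendance added only if p<0.05 | 0.27 | 0.50 | 74% |

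The last row is closest to the rule in section 14.1. The screen seldom admits attendance: in a parallel run with mean attendance 6.4 it did so in 8% of trials. When it does, the shift is large. The slope has SE 1/√73.5 = 0.117, so it must exceed about 2.01 × 0.117 = 0.235 to pass with a positive sign, and the intercept is then at or below about 0.40 − 6 × 0.235 = −1.01, the wrong direction.

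**Type I error.** With no true effect, screening and then reading the uncentred intercept gave 8.9% against 4.5% without attendance. The run with mean attendance 6.4 gave 8.5% against 4.6%, and a further rerun gave about 10%.

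**Where nothing happens.** With baseline and follow-up rows, a time term and attendance as a time-constant main effect, the time coefficient was 0.399 with or without attendance, significant in 81% of trials either way. Separately, selecting among 10–20 null covariates by outcome association moved type I error only from about 5% to 6% (n = 40).

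**Which case section 14.3 implies.** It cannot be settled from the text. Regression on time suggests a time coefficient. But the baseline value is also a covariate. If only follow-up rows enter, the time term contrasts 3 with 6 months and the change from baseline sits in the intercept, where coding matters.

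**The case against.** The strongest reply is that section 14.3 regresses outcomes on time, so the natural effect is the time coefficient, which an attendance main effect leaves alone in a linear model. The fall to zero needs three conditions together: the intercept as the effect, uncentred coding, and a change running wholly through sessions. The plan states none of them. This stands, and it limits the size of the point: a reader might infer that the rule will adjust the intervention effect away, and the documents do not support that. They only fail to exclude it.

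It is also true that the coding problem is not peculiar to attendance. In a change model with raw baseline (assumed mean 5) and raw social support (assumed mean 60), the intercept was 2.9; centring both returned 0.399. Fixing the covariate list alone would not cure this, so the remedy must also cover centring and name the effect. Under a non-linear link, which sections 14.1 and 14.3 leave open, covariate adjustment can change the estimand even when centred. That was not quantified and applies to baseline covariates too.

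Three further inferences go beyond the text. Study contacts are undefined, and section 8.3 describes reminders and cards, so they cannot be equated with dose. The group rule is undefined rather than impossible: recruitment source (section 8.1) or completion status could supply groups, but the plan names neither. And section 14.5 asks for sensitivity analyses on missingness; it does not require a comparison of completers with non-completers.

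None of this answers the textual point. Section 14.1 states an outcome-driven, post-baseline inclusion rule that conflicts with section 14.3.

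**Conclusion.** The point holds as a defect in the stated rule, worth correcting before analysis. Undefined groups, outcome-based admission of post-baseline variables, and the lack of reconciliation with section 14.3 all rest on the text alone.

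The numerical harm is conditional. It ranges from none to loss of the whole 0.40 SD estimate, with type I error of 9–10% in place of about 5% if the screen is applied at p<0.05 and the uncentred intercept is read. Those figures rest on the assumed attendance distribution, SD of change, threshold and session-driven effect.

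The outcomes affected are secondary. The primary feasibility and acceptability rates in section 14.2 are untouched.

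**What to change.** - Delete the group-difference and outcome-association rules from section 14.1.
- Fix the Aim 2 covariates in advance to the baseline values of the variables named in section 14.3, mean-centred. Specifying baseline matters because social support is measured again at 3 and 6 months (section 10.1).
- State in section 14.3 that the effect being estimated is the pre-post change from baseline.
- Report attendance, home practice and study contacts as feasibility results, or in a separately labelled exploratory dose-response analysis.
- Optionally, use the Fisher and t-tests to compare completers with non-completers, to inform the sensitivity analyses in section 14.5.

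The cost is wording only: no extra data, visits or participants. What is given up is the option to adjust for attendance in the main secondary models.

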### 14.2. Primary Outcomes: feasibility and acceptability

We will calculate retention and attendance rates as well as program satisfaction scores at 3 and 6 months.

Feasibility. We will consider either dose feasible under the following conditions:

If we achieve study retention rates of 80% at the last FU visit

If patients attend at least 70% of the planned classes

If patients report to have completed 70% of the assigned individual home practice exercises

Acceptability. A dose will be considered acceptable if at least 80% of participants will indicate grade 4 enjoyment ratings on a visual scale from 0 to 4 (4=high enjoyment; 0=no enjoyment).

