## STUDY AIMS

**Aim 1:** To determine the feasibility and acceptability of mobile phone-delivered MT in HF outpatients. Hypothesis: We will be able to reach our recruitment goal (n=50) within the study timeline, with < 20% drop out rates by the end of the study and > 80% of participants reporting high (=grade 4) enjoyment ratings on a scale from 0 to 4.

**Aim 2:** To determine whether mobile-delivered MT can improve self-reported and objectively assessed medication adherence as well as functional capacity (a clinical marker of medication adherence, per PA requirements). Hypothesis: we will observe significant pre-post intervention improvements in medication adherence and functional capacity.

**Aim 3:** To explore whether memory and attention change over time and whether such changes are associated with changes in medication adherence. The goal is to explore potential mediating effects that will be formally tested in a future fully powered RCT. We hypothesize for example, that MT will improve working memory, and that such changes will in turn be associated with improvements in adherence. Although measures of memory and attention are our primary posited mediators, we will also explore the role of mindfulness and depressive symptoms (additional potential mediators of MT effect).

## 5

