## ELIGIBILITY

### 7.1. Population

Participants (n=50) will be recruited from the HF clinic at Rhode Island Hospital (RIH), located in Providence, RI as well as among community dwelling adults in the Providence area.

Vulnerable populations. This study will not recruit individuals from vulnerable populations (i.e.: adults unable to consent, Infants, children, teenagers or pregnant women). Subjects with severe cognitive impairment (and thus, unable to provide informed consent) are excluded from participation in the study (see 9.2 for details).

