#### **14.4. Sample Size Considerations**

We aimed to obtain 80% power to detect a significant change over time in secondary outcome measures and potential mediators. Consistent with expert opinion, we integrated several sources of evidence to determine an expected effect size for power calculations. We based our estimates on (a) correlations between mindfulness and self-reported adherence from our prior work (see C.1) ( $\rho=0.68$ ,  $p<0.01$ ), (b) results from an observational study showing association between lapses in attention and adherence ( $OR=2.65$ ,  $p=0.02$ ) and (c) a longitudinal study ( $n=309$ ) among HF outpatients showing associations between memory and medication adherence ( $\beta=0.51$ ,  $p<0.01$ ). With  $n = 50$  and two-sided  $\alpha=0.05$  we will have 80% power to detect significant effects of MT on adherence, functional capacity, and mediator pathways (changes over time in mediators and their association with outcomes).

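### The primary feasibility and acceptability conclusions rest on point estimates without intervals, and Section 14.4 gives no precision for them at n=50

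*Combined protocol and SAP*

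**What the plan says.** Section 9.1 lists two primary outcomes, feasibility and acceptability. Section 14.2 plans to calculate retention, attendance and satisfaction, and then sets four conditions.

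- Retention: "If we achieve study retention rates of 80% at the last FU visit".
- Attendance: "If patients attend at least 70% of the planned classes".
- Home practice: "If patients report to have completed 70% of the assigned individual home practice exercises".
- Enjoyment, the fourth condition: "A dose will be considered acceptable if at least 80% of participants will indicate grade 4 enjoyment ratings".

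Neither Section 14.2 nor the rest of Section 14 gives an interval, test, error rate or precision target for these outcomes. Section 14.4 opens with its purpose: "We aimed to obtain 80% power to detect a significant change over time in secondary outcome measures and potential mediators". It says nothing about what n=50 delivers for the primary outcomes.

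Aim 1 states the two 80% targets differently: "with < 20% drop out rates by the end of the study and > 80% of participants reporting high (=grade 4) enjoyment ratings".

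The study has a single arm (Section 8.2: "This is a pre-post design study. NO randomization is involved"), with 50 participants planned (Section 7.1).

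**The concern.** A pilot of this kind exists mainly to say whether the programme can be delivered and is liked well enough to take into a full trial. Under Section 14.2 that answer is a yes or no read from an observed rate. With 50 people the rate carries an uncertainty of more than ten points on the low side, and the plan neither reports this nor lets it qualify the conclusion. A reader told only that the 80% retention criterion was met would not know that the data are also compatible with retention well below 80%. A narrow miss would likewise hide compatibility with retention well above it.

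The one-participant gap between Aim 1 and Section 14.2 adds a practical problem: at exactly 40/50 the protocol gives two opposite answers about its own primary outcome.

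**Working it through.** **Inputs.** n = 50 (Section 7.1). Retention and enjoyment cut-offs of 80% and attendance and home-practice cut-offs of 70% (Section 14.2). Strict forms of the two 80% targets (Aim 1). The true rates used below are illustrative, since the documents assume none. The plan gives no precision or power figure for the primary outcomes, so there is none to reproduce.

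**Step 1. Cut-offs as counts.** Reading the retention condition as at least 80%, Section 14.2 needs 0.80 × 50 = 40. Under Aim 1, fewer than 20% dropping out means fewer than 10 of 50, so at least 41 retained; more than 80% at grade 4 means at least 41 of 50.

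**Step 2. Precision.** The exact (Clopper-Pearson) 95% limits for x out of n are the 2.5% quantile of Beta(x, n−x+1) and the 97.5% quantile of Beta(x+1, n−x).

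| Observed | Rate | Exact 95% interval |
|---|---|---|
| 40/50 | 80% | 66.3% to 90.0% |
| 41/50 | 82% | 68.6% to 91.4% |
| 32/40 | 80% | 64.4% to 90.9% |
| 35/50 | 70% | 55.4% to 82.1% |

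At 40/50 the limits lie 80.0 − 66.3 = 13.7 points below the estimate and 90.0 − 80.0 = 10.0 above. The 32/40 row shows enjoyment if only retained participants rate it and retention is 80%; the plan does not state that denominator. The 35/50 row applies to attendance or practice only if the criterion is a proportion of patients, which is also not stated.

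**Step 3. How the rule behaves.** P(pass) = P(X ≥ c) with X ~ Binomial(50, p).

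| True rate p | c = 40 (Section 14.2) | c = 41 (Aim 1) |
|---|---|---|
| 70% | 7.9% | 4.0% |
| 75% | 26.2% | 16.4% |
| 80% | 58.4% | 44.4% |
| 85% | 88.0% | 79.1% |
| 90% | 99.1% | 97.5% |

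The rule is reliable at 70% and at 90%. Its uncertain zone is roughly 75% to 85%.

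**Step 4. The strict and non-strict forms.** They differ only when exactly 40 of 50 succeed. At a true 80% that has probability 58.4 − 44.4 = 14.0%, so the conflict could well arise.

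**The case against.** Pre-stated cut-offs are a legitimate choice for a single-arm pilot, and nothing in Section 14.2 prevents intervals from being reported. Both points stand, and the cut-offs need not be abandoned. But the plan does not commit to intervals, and its decision wording takes no account of them.

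Stronger readings are tempting and do not hold.

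- A reader might infer from the 58% at a true 80% that the decision is a coin toss because n=50 was badly justified. A pass chance near one half at the cut-off occurs at any sample size: the same calculation gives 54% at n=200 and 52% at n=1000. What n=50 sets is the width of the uncertain zone.
- A reader might infer from the interval for 40/50 that the rule cannot tell retention of two thirds from nine tenths. Those values are only the limits around one observed result. The rule passes about 3% of the time at a true two thirds and 99% at 90%.
- A reader might multiply the chances of passing retention and enjoyment. Section 14.2 judges feasibility and acceptability separately and sets no joint rule, and independence would be an unsupported assumption.
- A reader might suppose that a later trial's attrition allowance will be taken from this point estimate. The documents do not say so.

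Nor should the remedy become a requirement that the whole interval clear 80%. That needs 46/50 (lower limit 80.8%; at 45/50 it is 78.2%), which has only a 43% chance even at a true 90%.

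**Conclusion.** The point holds as a matter of how the primary conclusion is drawn and reported. Feasibility and acceptability are declared from point estimates alone, and the sample-size section gives no precision for them. At an observed 40/50 the uncertainty is about −14/+10 points, and the pass probability runs from 26% to 88% between true rates of 75% and 85%. It does not invalidate the design or show that n=50 is too small, since the rule separates 70% from 90% well.

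These figures assume independent participants, all 50 enrolled, and all 50 in the denominator. For enjoyment the denominator may be smaller and the interval wider. For attendance and home practice the binomial figures apply only if the criteria count patients. The conflict between Aim 1 and Section 14.2 at 40/50 needs no such assumptions beyond n=50 as the common denominator.

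**What to change.** **Section 14.2.** Keep the cut-offs as progression targets. Report retention and grade 4 enjoyment with exact 95% intervals, and state the feasibility and acceptability conclusions together with those intervals. Specify whether the enjoyment denominator is everyone enrolled or only those who give a rating. Define attendance and home practice either as the proportion of patients reaching a stated level, with an exact interval, or as an average percentage per patient, with an interval for a mean. Sessions should not be pooled across patients as if they were independent.

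**Section 14.4.** Add the precision that n=50 gives for the primary outcomes: about −14/+10 points at an observed 40/50.

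**Aim 1 and Section 14.2.** Reconcile the inequalities so that one count defines success for retention and one for enjoyment.

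**Cost.** Changes to wording, definitions and a few intervals, with no added patients, visits or data. The downside is that the feasibility claim will be stated less firmly.
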